- 7) Hospice designation (either currently in hospice or previously enrolled within the past 30 days)

B. Data Collected:

The data elements of interest include, but are not limited to the following:

1. *Patient information*
 - a. Name

- b. Date of birth
- c. Medical record number
- d. Phone number
- e. Primary diagnosis
- f. Relevant social and family history
- g. Previous medical history such as clinic notes, current medications, results of all tests, procedures and laboratory assessments.
- h. Medications
- i. Weight and height

2. *Transthoracic echocardiogram (TTE)*
3. *Hemodynamics via pulmonary artery catheter*
 - a. RA pressures
 - b. RV pressures
 - c. PA pressures
 - d. Pulmonary capillary wedge pressure (PCWP)
 - e. Fick cardiac output and cardiac index
 - f. Systemic vascular resistance (SVR)
 - g. Pulmonary vascular resistance (PVR)
 - h. Cardiac power and cardiac power index
 - i. Mixed venous saturation (MVO₂)
4. *Metabolic parameters*
 - a. Serum lactate level
 - b. Basic metabolic panel - Renal function and serum electrolytes
 - c. Hepatic function
 - d. Coagulation parameters
 - e. Complete blood count (CBC)
 - f. Arterial blood gas (ABG)
5. *Physiologic parameters and vital signs*
 - a. Urine output
 - b. Blood pressure
 - c. Heart rate
 - d. Bladder or esophageal temperature
 - e. Respiratory rate
6. *Electrocardiogram*
7. *Vasoactive medication requirements*
 - a. Cumulative inotrope (i.e. milrinone, dobutamine) and vasopressor (i.e. norepinephrine, phenylephrine, dopamine, vasopressin) doses
8. *Blood samples for future research*
 - a. Stored without identifying information for future research, which may include genetic testing

- b. May be shared with outside collaborators for research purposes, with identifiers removed

C. Timing of Data Collection:

Baseline parameters (prior to initiation of cooling):

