5. TTE
6. Blood sample for future research

Endpoints

Primary safety endpoints:

1. Arrhythmia requiring medical therapy or therapy with temporary pacemaker
2. Bleeding requiring transfusions as a direct result of the cooling catheter insertion or secondary to resulting coagulopathy
3. Clinically important bloodstream infection, as confirmed with 2 positive blood cultures, or suspected sepsis in the absence of positive blood cultures with a sequential organ failure assessment (SOFA) score >2
4. Hypokalemia with potassium levels below 3.0mEq/L, not secondary to other identifiable causes

Secondary endpoints:

1. Hemodynamic changes during intervention period – Cardiac output/Cardiac Index, PCWP, SVR, mixed venous oxygen saturation (MVO₂), cardiac power index
2. Cumulative vasopressor and inotrope dose requirements (i.e. number of vasoactive and/or inotropic drugs used)
3. Echocardiographic % change in ejection fraction at 18-24 hours (from baseline)
4. In-hospital all-cause mortality

Procedures

Patients admitted to the Coronary Care unit (CCU) at the University of Chicago will be screened by the study investigators and the cardiology fellow on the CCU rotation. Patients meeting the inclusion criteria, as defined previously, will be identified and randomized after informed consent within 12 hours of presentation. Patients will be randomized to either TH plus standard medical care or to standard medical care alone. A pulmonary artery (PA) catheter will be placed at the bedside or in the Cardiac Cath lab if difficult anatomy is anticipated. As mentioned earlier, placement of a PA catheter is part of the standard of care for management of cardiogenic shock. Currently, patients who are admitted to the University of Chicago CCU with cardiogenic shock routinely undergo placement of PA catheter by the cardiology fellow in the CCU or in the cardiac cath lab. Data from the PA catheter is vital in initiating vasopressors/inotropes, assessing the response to the therapies, and possible need for escalation of therapy (i.e. mechanical support). In this study, patients in each arm will undergo PA catheter placement.

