administration of medications or a dialysis catheter for temporary dialysis. After successful insertion of the cooling catheter, it will be connected to the Thermogard XP® thermal regulation system. The Quattro® catheter functions as both a central venous triple lumen catheter as well as a cooling catheter. Cooling is achieved by circulating normal saline in a closed system through the catheter. The flow and temperature (range 4°C to 42°C) of the circulating saline serves as the heat exchange mechanism and is controlled by the external Thermoguard® thermal regulation system. The temperature is measured and adjustments are made by the thermal regulation system to automatically maintain target temperature. The target temperature is achieved within 2-3 hours of initiation of TH. Rewarming is accomplished using the same balloon catheter system and heat exchange occurs without infusion of any saline or fluids into the patient. In clinical trials, intravenous catheter based cooling system has been shown to achieve target temperature faster and maintain target temperature with more precision.^{12,14,15}

Medical therapy in both intervention and non-intervention groups will be based on the current recommendations for management of cardiogenic shock. This includes inotropic therapy (i.e. dobutamine or milrinone) for cardiac support, vasopressor therapy (i.e. norepinephrine, dopamine, phenylephrine, epinephrine) to achieve target blood pressure (mean arterial blood pressure \geq 60 mmHg), diuretics for volume removal, and mechanical circulatory support as clinically indicated. All patients included in this study will have pulmonary artery (PA) catheters inserted within 12 hours of randomization via either the internal jugular or femoral venous approach to monitor real-time hemodynamics. The clinicians in the CCU will use the data from PA catheters (cardiac output, mixed venous saturation, systemic vascular resistance, etc.) to guide therapy for both the intervention and non-intervention groups. The primary investigator of this study ([name]) will have no role in the clinical management of the patients.

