Laboratory, echocardiographic, and hemodynamic parameters will be obtained for patients prior to randomization, near the end of 24 hour cooling therapy, and after 48-96 hours post-randomization. Core temperature will be measured via either thermal tip at the end of a transurethral urinary catheter or endotracheal temperature probe in intubated patients. Rewarming will be accomplished at 0.3°C per hour until temperature reaches 37°C.

Target Enrollment and Study Duration

In this initial pilot study, we anticipate enrolling 20 patients to the study, 10 randomized to standard medical therapy and 10 patients randomized to standard medical therapy and 24 hours of TH. We anticipate completing enrollment within 6 months.

Statistical Methods

The three-dichotomous primary endpoints will be analyzed using a two-sample independent proportion test or a Fisher's exact test with a Bonferroni method continuity correction for multiple endpoints. Furthermore, numerical secondary endpoints will be presented as either

mean \pm standard deviation or median (interquartile range) based upon the distribution of the data. In addition, all numerical secondary endpoints will be assessed using two independent t tests or Mann-Whitney U test for comparisons. Categorical variables will be tested with chi-square tests of association or Fisher's exact tests. Differences will be considered significant using an alpha value of 0.05 for a two-sided test. Analyses will be performed using STATA MP Version 14 (College Station, TX).

Potential risks and benefits to subjects

A. Benefits:

There is mounting evidence that TH has positive effects on cardiac function. Multiple studies have suggested that TH may offer particular benefit in cardiogenic shock. In this prospective trial, the patients will be randomized to TH or standard medical care using simple randomization. With TH, we expect increased cardiac output, increased contractility, lower SVR, and higher cardiac power index which will lead to improved hemodynamics and potentially decreasing pressor requirements.

B. Risks:

Anticipated adverse events that could possibly occur during the study include, but are not limited to:

1. *Risks associated with TH*
 - a. Shivering
 - b. Arrhythmia
 - c. Coagulopathy with or without clinically significant bleeding
 - d. Hyperglycemia
 - e. Hypothermia
 - f. Electrolyte abnormalities
 - g. Infections
2. *Risks associated with cooling catheter insertion*
 - a. Bleeding
 - b. Infection

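### Hemodynamic and EF secondary endpoints have a baseline, but are compared by unadjusted tests on an incompletely defined quantity; baseline-adjusted ANCOVA would be valid, cheap and usually more precise

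*Combined protocol and SAP*

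**What the plan says.** - **Analysis.** Statistical Methods: "all numerical secondary endpoints will be assessed using two independent t tests or Mann-Whitney U test for comparisons", two-sided at 0.05. Neither ANCOVA nor any other regression on baseline appears in the document.
- **Endpoints.** The secondary list includes "Hemodynamic changes during intervention period" (cardiac output/index, PCWP, SVR, mixed venous saturation, cardiac power index) and "Echocardiographic % change in ejection fraction at 18-24 hours (from baseline".
- **Data available.** Section C (Timing of Data Collection) and Appendix 1 schedule echocardiography and hemodynamics at baseline, at 18-24 hours and at a later visit. Vasoactive dosing has no baseline entry.
- **When baseline is read.** Section C heads the list "Baseline parameters (prior to initiation of cooling". Procedures states in one place that "hemodynamic parameters will be obtained for patients prior to randomization". In another place it describes randomization and then says "A pulmonary artery (PA) catheter will be placed at the bedside". In a third it has "catheters inserted within 12 hours of randomization", without saying before or after.
- **Size and allocation.** 20 patients, 10 per arm, by simple randomization.

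**The concern.** A two-sample test on follow-up values ignores the baseline. A test on change scores subtracts it with a fixed coefficient of 1, whatever the correlation. ANCOVA estimates the coefficient, so it usually gives a tighter comparison from data the trial already collects. The Objective section names understanding the physiologic effects of hypothermia as an aim, and these comparisons are the trial's output on that aim. With about 20 patients, or fewer if some die before the 18-24 hour reading, precision is scarce.

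Two further issues follow.

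- **The tested quantity is open.** Change scores are the likeliest reading for hemodynamics, but absolute or relative is not stated. For EF, the variable, time and reference are fixed, but % change can mean relative change or EF percentage points. In an unblinded trial this leaves room to choose after the data are seen.
- **The hemodynamic baseline must precede randomization in every patient.** Many patients will probably have such a reading: the protocol says shock patients "routinely undergo placement of PA catheter by the cardiology fellow", and cardiac index and PCWP are listed entry criteria. It is not assured for all, because the prose definition under Patient Population joins those criteria with 'or'. Start of cooling is also an anchor that control patients do not have.

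**Working it through.** **Inputs from the documents:** 10 per arm, two-sided alpha 0.05, simple randomization. No power, SD, effect size or baseline/follow-up correlation (ρ) is given, so there is no planned figure to reproduce. **Assumed:** effect 1 SD, equal SDs at both times, normal data, ρ from 0 to 0.9.

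**Formulas.** Let N = n1 + n2 and h = 1/n1 + 1/n2, with variances in SD² units.

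- Follow-up value: variance h, noncentral t on N−2 df.
- Change score: variance 2(1−ρ)h, N−2 df.
- ANCOVA: variance (1−ρ²)h(1 + F/(N−2)), averaged over F ~ F(1, N−2), on N−3 df. The mean inflation is 1 + 1/(N−4), which is 1 + 1/16 = 1.0625 at N = 20.

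**Power and mean 95% CI half-width (in SD) at 10/10**, each as follow-up / change / ANCOVA:

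| ρ | Power | CI half-width |
|---|---|---|
| 0 | 0.56 / 0.32 / 0.54 | not computed |
| 0.3 | 0.56 / 0.43 / 0.57 | 0.93 / 1.10 / 0.91 |
| 0.5 | 0.56 / 0.56 / 0.66 | 0.93 / 0.93 / 0.83 |
| 0.7 | 0.56 / 0.78 / 0.82 | 0.93 / 0.72 / 0.68 |
| 0.8 | 0.56 / 0.92 / 0.93 | 0.93 / 0.59 / 0.57 |
| 0.9 | 0.56 / 1.00 / 1.00 | 0.93 / 0.41 / 0.42 |

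**Break-even on variance.**

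- Against the follow-up value: (1−ρ²)(N−3)/(N−4) = 1 gives ρ = √(1/(N−3)) = √(1/17) = 0.24.
- Against the change score: (1−ρ²)(N−3)/(N−4) = 2(1−ρ) gives ρ = 2(N−4)/(N−3) − 1 = 32/17 − 1 = 0.88. Allowing for the lost degree of freedom, the break-even on power at 1 SD is about 0.85, and the loss between 0.85 and 0.88 is at most 0.1-0.2 point.

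**Fewer evaluable patients.** At 8/8, power is 0.46/0.46/0.54 at ρ 0.5, 0.46/0.67/0.70 at 0.7 and 0.46/0.84/0.84 at 0.8. On variance, ANCOVA beats both alternatives for ρ of 0.28-0.85 at 8/8 and 0.30-0.82 at 7/7.

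**Uneven arms.** Simple randomization of 20 gives exactly 10/10 with probability C(20,10)/2²⁰ = 0.18. Averaged over the splits, power is 0.54/0.41/0.55 at ρ 0.3, 0.54/0.54/0.64 at 0.5 and 0.54/0.76/0.80 at 0.7.

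**Type I error of ANCOVA**, simulated at N = 20: 4.6-5.7% with normal data and 4.8% with lognormal data (Monte Carlo SE about 0.4 points).

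**EF simulation** (30,000 runs per cell, 48 cells, 10/10, constant 6-point effect). All inputs are assumed: reduced EF mean 25, SD 7; preserved EF mean 58, SD 5, in 0-30% of patients; reading SD 4-6; lowest EF 5-12; extra follow-up SD 3.

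- Relative % change: power 0.19-0.44.
- Change in EF points: 0.29-0.52.
- ANCOVA: 0.29-0.53.

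The relative form loses 6-13 points against ANCOVA (7-20 if the effect is proportional, at 24% of EF). The EF-point form is within −4 to +2 points of ANCOVA.

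**The case against.** The planned tests are valid, the trial is a safety pilot, and neither its sample size nor any decision rule depends on these comparisons. On that view ANCOVA is a preference. ρ is unknown, and entry limits on cardiac index and PCWP could restrict the baseline range and lower it. Against a change score, the likeliest reading, the gain is only 4 points at ρ 0.7 and 1 at 0.8. At 5/5 evaluable the advantage nearly vanishes: 0.29 against 0.32 at ρ 0.5, equal at 0.7 (0.44 each), and 0.59 against 0.57 in favor of the change score at 0.8. Every EF input is assumed, and the loss arises only if % change is relative. The Procedures section does state a pre-randomization baseline, so the timing question is partly answered and bears equally on a change score. ANCOVA does nothing for values missing through death.

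All of this stands as limits on size. It does not reverse the point. A low ρ weakens the case against follow-up values but strengthens it against change scores. With ρ unknown, ANCOVA is the choice with the smallest regret at 10/10: at worst about 3 points, at ρ 0 against the follow-up value. A wrong unadjusted choice can cost 21 points (change score at ρ 0, 0.54 − 0.32 before rounding) or 26 (follow-up value at ρ 0.7). The 5/5 case is extreme, because the 50% mortality in the Background is an upper figure for the whole index hospitalization after infarction, not loss by 24 hours. The open definition of the tested quantity depends on no assumed correlation.

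**Conclusion.** The concern holds, as a modest efficiency and pre-specification point on secondary endpoints. It is not a validity problem. For an assumed 1-SD effect at 10/10, ANCOVA gains about 10 points of power over either alternative at ρ 0.5. Against a change score the gain shrinks to 4 points at 0.7 and 1 at 0.8, and is gone by about 0.85-0.88. Against the follow-up value there is no gain below about 0.24. For EF, the loss is 6-13 points if % change is relative and little or none if it means EF points, under assumed distributions. These sizes depend on correlations and SDs that the documents do not give. Two findings do not: the scale of the tested quantity is not stated, and the statements on hemodynamic baseline timing need reconciling whichever analysis is used.

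**What to change.** 1. Analyse cardiac output/index, PCWP, SVR, mixed venous saturation, cardiac power index and EF at 18-24 hours by ANCOVA, with arm and that variable's own baseline as terms. Report the adjusted difference with its 95% CI. Name a rank-based version in advance as supportive, for use if residuals are skewed.
2. Use EF at 18-24 hours adjusted for baseline EF in place of % change. Percent change may stay as a descriptive summary if the plan says whether it is relative or in EF points.
3. Leave cumulative vasoactive requirement unadjusted, since no baseline is collected.
4. Reconcile the Procedures statements on catheter placement with the statement that hemodynamics are obtained before randomization, so that the covariate is a pre-randomization value defined identically in both arms.
5. State a rule for patients without such a value, for example the overall mean of the observed pre-randomization values, ignoring arm.

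Cost: wording in the Statistical Methods and Procedures sections, and one degree of freedom (18 to 17 at 10/10). About 3 power points are lost against follow-up values if ρ is near 0, and a change score is marginally better at very high ρ. No additional measurement is needed where the baseline reading is already taken before randomization.

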All patients meeting criteria for cardiogenic shock (defined as systolic blood pressure <90mmHg for at least 30 minutes, Cardiac Index < 2.2 L/min/m², pulmonary capillary wedge pressure (PCWP) ≥ 15mmHg, need for vasopressors, or need for mechanical support to keep systolic blood pressure ≥ 90mmHg) admitted to the University of Chicago Coronary Care Unit (CCU) will be randomized to standard medical therapy or to therapeutic hypothermia (32-34°) for 24 hours plus medical therapy in a non-blinded manner with 1:1 randomization using computer-generated random numbers (simple randomization). The cardiogenic shock may be a result of acute coronary syndromes (STEMI, NSTEMI, or UA), ischemic or non-ischemic cardiomyopathy, myocarditis, hypertrophic cardiomyopathy, stress-induced cardiomyopathy, peripartum cardiomyopathy, or cardiogenic shock in a patient with HF with preserved EF. Patients less than 18 years of age or greater than 89 years of age will be excluded. Patients with

baseline heart rate less than 60 beats per minute, baseline temperatures less than 35°C, recent cardiotomy, history of cardiac transplantation, or those who are pregnant will be excluded.

All patients between the ages of 18 and 89 who meet the criteria for cardiogenic shock in the CCU will be screened. Inclusion and exclusion criteria are listed below.

Inclusion Criteria:

- 1) Cardiogenic shock
 - a) Systolic blood pressure <90mmHg for at least 30 minutes
 - b) Cardiac Index < 2.2 L/min/m²
 - c) Pulmonary capillary wedge pressure (PCWP) ≥ 15mmHg
 - d) Need for central venous access, vasopressors, inotropes and/or mechanical circulatory support (i.e. intra-aortic balloon pump, Impella, ECMO) to maintain systolic blood pressure ≥ 90mmHg
- 2) Etiology of shock
 - a) Acute coronary syndromes (STEMI, NSTEMI, or UA)
 - b) Ischemic or non-ischemic cardiomyopathy
 - c) Myocarditis
 - d) Hypertrophic cardiomyopathy
 - e) Stress-induced cardiomyopathy
 - f) Peripartum cardiomyopathy
 - g) Cardiogenic shock in a patient with HF with preserved EF
- 3) Age ≥ 18 years AND ≤ 89 years
- 4) Admission to the University of Chicago CCU

Exclusion Criteria:

- 1) Baseline heart rate < 60 beats per minute
- 2) Baseline temperatures < 35°C
- 3) Recent cardiotomy
- 4) History of cardiac transplantation
- 5) Current pregnancy
- 6) Contraindication to 9.3 French femoral venous access for placement of intravascular cooling catheter

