 - c. Vascular injury

Mitigating Risks associated with TH:

Shivering is the most common risk associated with TH. Shivering is a normal physiological response to cooling as it allows the body to expend energy and generate heat. This leads to increasing metabolic demands and subsequent oxygen consumption. Various strategies can be used to combat shivering and have these have been well described in the literature. In patients that are intubated, the most common means of combating shivering is a combination of benzodiazepines, opioid analgesics, and/or neuromuscular blockade.¹⁶ In awake patients, combination of meperidine and warming of skin with air-warming products such a 'Bair Hugger

blanket' (3M, St. Paul, MN) hugger' are utilized.¹⁷ Meperidine is the most beneficial agent to prevent shivering and previous studies have demonstrated significant lowering of the shivering threshold with meperidine.^{17,18} Given that intravascular cooling therapy is common in multiple ICU settings, including the cardiac care unit (CCU), protocols are already in place for the management of shivering, with an institutional-approved anti-shivering protocol often used in patients undergoing TH.¹⁸ In the event of persistent shivering despite therapy with intravenous sedatives, anesthetics (i.e. propofol or meperidine) and/or paralytic agents in intubated patients, the TH protocol will be stopped and patients will be rewarmed to normothermia.

Therapeutic hypothermia may potentially increase the risk of arrhythmias and will be evaluated in this trial. Bradycardia is expected with TH. In the previously published studies, the reduction in heart rate is not significant enough to cause hemodynamic compromise.^{9,17,19} However, if a patient is noted to be persistently bradycardic, with signs or symptoms requiring temporary pacemaker insertion, the TH protocol will be stopped. Bradycardia requiring temporary pacing will be considered an adverse event of cooling if the patient did not have underlying conduction system disease (i.e. first or second degree AV block) prior to cooling. In such cases, patients will be rewarming to normothermia per the rewarming protocol currently in place for intravascular cooling of critically ill patients.

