The DSMB will meet (in person or via telephone conference) a minimum of 3 times:

- after treatment of the first 4 subjects (2 in the TH arm and 2 in the control arm)
- after treatment of the first 10 subjects (5 in the TH arm and 5 in the control arm)
- at the conclusion of the study

The DSMB may convene additional meetings if necessary to ensure the ongoing monitoring and safety of the subjects treated with TH.

A quorum of at least two (2) DSMB members needs to be present for a meeting to commence. Members may either be present in person or have the option to phone-in if unable to arrive at the meeting location.

All DSMB members will receive an agenda prior to the meeting. In the event that a DSMB member is unable to attend a meeting, that member will receive minutes, as well as any additional notes, with the opportunity to share any additional thoughts on the distributed information.

5. Grading and Attribution Methods for Adverse Events

Grading Scale

The DSMB and the study team will utilize the Adverse Event Grading Scale provided in Table A. All adverse events will be graded according to this scale, the PI will prepare data regarding adverse events for review by the DSMB prior to meeting, and any additional details will be provided to the DSMB by the PI, as necessary.

Table A – Safety Reporting Definitions

Term	Definition
Adverse Event (AE) Ref: ISO 14155-2011 Ref: MEDDEV 2.7/3 12/2010	
Any untoward medical occurrence, unintended disease or injury, or any untoward clinical signs (including an abnormal laboratory finding) in subjects, users or other persons, whether or not related to the investigational medical device.
 
This definition includes events related to the procedures involved (any procedure in the clinical investigation plan).

Adverse Device Effect (ADE) Ref: ISO 14155-2011 Ref: MEDDEV 2.7/3 12/2010	
Adverse event related to the use of an investigational medical device
 
NOTE 1: This definition includes any adverse event resulting from insufficient or inadequate instructions for use, the deployment, the implantation, the installation, the operation, or any malfunction of the investigational medical device.
 
NOTE 2: This definition includes any event resulting from use error or from intentional misuse of the investigational medical device.

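### Pacing for bradycardia in patients with prior AV block is denied the label of a cooling event by a blanket rule, which conflicts with the charter's relatedness criteria and understates the cooling-attributed safety tally

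*Combined protocol and SAP*

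**What the plan says.** **Eligibility.** The only exclusion that concerns heart rate or conduction is item 1 of the Exclusion Criteria: "Baseline heart rate < 60 beats per minute". AV block is not listed.

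**Expected effect and attribution.** The bradycardia paragraph under Mitigating Risks associated with TH states "Bradycardia is expected with TH". For a persistently bradycardic patient "with signs or symptoms requiring temporary pacemaker insertion, the TH protocol will be stopped", with no exception for AV block. The attribution rule follows: "Bradycardia requiring temporary pacing will be considered an adverse event of cooling if the patient did not have underlying conduction system disease". First- or second-degree AV block before cooling is named in brackets.

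**Primary safety endpoint 1.** "Arrhythmia requiring medical therapy or therapy with temporary pacemaker". It has no causality clause. Endpoint 4 does have one: "Hypokalemia with potassium levels below 3.0mEq/L, not secondary to other identifiable causes".

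**Collection and review.** The Data Safety Monitoring Board section collects treatment-emergent events regardless of relatedness, has the DSMB told of bradycardia that ends the protocol, and gives it final adjudication.

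**Charter (Appendix 2, section 5).** Table A defines an adverse event "whether or not related to the investigational medical device" and defines an adverse device effect separately. The note after Table A makes an underlying disease reportable once it becomes more severe or more frequent. Under Table B, an event is Related when another cause is no more likely than the device.

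**The concern.** A patient with AV block and a rate of 70 can be randomized to an intervention that the protocol expects to slow the heart. If that patient then needs a temporary pacemaker, the rule keeps the event out of the count of cooling events, whatever its timing or course. The stated objective is to establish the safety and tolerability of hypothermia in the population enrolled. An attribution rule that always resolves in favour of the intervention, in the patients where the question is hardest, weakens the main product of a pilot: its descriptive safety summary.

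There is also a scoring risk. The trial is unblinded, and the principal investigator classifies events and prepares the causality analysis for the DSMB. If the rule were read as part of the definition of endpoint 1, it could act only on cooled patients. A control patient with AV block who is paced would still count.

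**Working it through.** **Step 1: the passages side by side**

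| Place | Treatment of pacing in a cooled patient with prior AV block |
|---|---|
| Mitigating Risks, attribution sentence | By implication, not an adverse event of cooling |
| Mitigating Risks, stopping sentence | Cooling stops; no AV-block exception |
| Primary safety endpoint 1 | Counts, in either arm |
| Data Safety Monitoring Board section | Collected, and sent to the DSMB because cooling stopped |
| Table A | An adverse event, related or not |
| Note after Table A | Reportable if the underlying disease worsens |
| Table B | Related if the alternative cause is equally or less likely |

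The conflict with Table B is direct: one text decides in advance and the other weighs the case. The conflict with the underlying-disease note is looser, since that note governs reporting and not attribution. But every enrolled patient starts at 60 or more, so, unless the patient was already paced, bradycardia that needs pacing is a worsening. The attribution sentence does not say that such an event remains reportable.

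**Step 2: size per event.** Target Enrollment plans 10 patients per arm, so k relabelled events lower the cooling-attributed rate by k/10: 10 percentage points for k = 1 and 20 for k = 2. If two cooled patients with AV block are paced and no others are, the attributed tally falls from 2/10 (exact 95% CI 3% to 56%) to 0/10 (0% to 31%).

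**Step 3: illustration.** The plan gives no figure to reproduce, and all three inputs here are assumptions: AV-block share f = 10% to 30%; pacing risk with AV block p1 = 20% to 40%; pacing risk without it p0 = 5% to 10%.

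- Rate over all pacing events: f·p1 + (1 − f)·p0
- Rate labelled as cooling events: (1 − f)·p0
- Share withheld: f·p1 / [f·p1 + (1 − f)·p0]
- Chance of at least one event in 10 patients: 1 − (1 − rate)^10

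| f | p1 | p0 | All | Labelled | Withheld | At least one: all | At least one: labelled |
|---|---|---|---|---|---|---|---|
| 0.1 | 0.2 | 0.05 | 6.5% | 4.5% | 31% | 49% | 37% |
| 0.1 | 0.2 | 0.10 | 11% | 9% | 18% | 69% | 61% |
| 0.3 | 0.4 | 0.05 | 15.5% | 3.5% | 77% | 81% | 30% |
| 0.3 | 0.4 | 0.10 | 19% | 7% | 63% | 88% | 52% |

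Over the whole grid, 18% to 77% of expected pacing events lose the label. The expected count for endpoint 1 as worded does not change.

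**Step 4: formal tests.** The Bonferroni level is 0.05/4 = 0.0125 for the four endpoints listed, or 0.05/3 = 0.0167 for the three that Statistical Methods mentions. Two-sided Fisher's exact tests with 10 per arm give p = 0.47 for 2 v 0, 0.0325 for 5 v 0 and 0.0108 for 6 v 0. With no control events, 6 v 0 is needed at either level. One or two relabelled events would rarely decide a test; the effect is on the descriptive summary.

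**The case against.** The strongest reply is that nothing is hidden. Endpoint 1 has no attribution clause, and where the authors wanted one they wrote it in, as in endpoint 4 and in the direct-result wording of endpoint 2. Any patient who needs pacing stops cooling, and bradycardia that stops cooling goes to the DSMB. All of this stands. A reader might infer that the risk in AV-block patients is concealed, that the DSMB sees a reduced count, or that a true 2/10 versus 2/10 would be reported as 0/10 versus 2/10. The documents do not support these readings. The last requires both paced patients in the cooled arm to have had AV block, and also the attribution rule to be used to score endpoint 1, which the plan does not say.

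A second reply is that Table A is not contradicted. This also stands: an event can be an adverse event without being attributed to cooling. Likewise, only cooled patients can have an event of cooling, so the one-sidedness of the label is not in itself a between-arm bias.

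Two things remain. The blanket rule does not fit Table B. And the plan does not say which text governs endpoint 1: the hypokalemia definition in the same risk section is almost identical to endpoint 4, so a scorer could reasonably take that section as supplying endpoint definitions.

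**Conclusion.** The concern holds as a problem of attribution. The rule understates the cooling-attributed tally by 10 percentage points per affected event, and it contradicts the charter's own relatedness criteria. How many events are affected cannot be known from the documents; the 18% to 77% range rests wholly on assumed inputs. Loss of events from primary endpoint 1 is a risk of misapplication and does not follow from the plan as written. Formal test results would rarely change. The point still deserves correction because it concerns a stated rule in a trial whose purpose is safety, and because it is better settled before events are classified in an unblinded study.

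**What to change.** Reconcile the attribution sentence with endpoint 1, the underlying-disease note and Table B:

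1. Delete the blanket conduction-disease condition and attribute these events by the Table B criteria, with DSMB adjudication as already planned.
2. State under Endpoints that endpoint 1 counts all new temporary pacing and all treated arrhythmia after randomization, in both arms, regardless of baseline conduction disease.
3. Record AV block from the baseline ECG already scheduled in Appendix 1, and report these events by that status.

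The cost is one sentence removed, one added and one baseline data field. The downside is a possibly higher reported event rate in the cooled arm. None of this requires a change in who is enrolled or how patients are managed; both remain with the investigators.
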